5.2 Discussion of Trial Design

This clinical trial is being proposed in response to the Chinese Health Authority which requested that a randomized controlled trial be performed for local registration proposes.

The use of cetuximab plus platinum-based chemotherapy as first-line treatment of subjects with recurrent and/or metastatic SCCHN has been investigated in a number of trials. The treatment duration, control group, and treatment allocation designed for this trial are similar to those in the largest trial, the EXTREME trial (EMR 62 202-002), which confirmed the benefit of adding cetuximab to platinum-based chemotherapy in the first-line treatment of subjects with recurrent and/or metastatic SCCHN. The dose of cisplatin and 5-FU applied in this trial has been modified according to local clinical practice (cisplatin dose intensity decreased by 25% and 5-FU dose intensity decreased by 6.25% compared with that in the EXTREME trial) (33).

If cisplatin results in a nonhematologic toxicity (see Section 6.4.1.2.2), cisplatin may be replaced by carboplatin in subsequent cycles. The dose of carboplatin in this trial is the same as that in the EXTREME trial, which is accepted by Chinese Investigators (33).

The primary endpoint in this trial is PFS time, as assessed by an IRC. While OS time is still considered the 'gold standard' of clinical efficacy, PFS time has been recommended in SCCHN trials as a primary endpoint. A recently published trial analyzed aggregate data from all published phase III clinical trials (ECOG, EXTREME, and SPECTRUM) using EGFR monoclonal antibodies as first-line treatment in recurrent and/or metastatic SCCHN, to investigate PFS time as a surrogate endpoint to OS time. The limited data indicated a linear relationship between PFS time and OS time with a constant difference between them of 5 months. This data suggested that PFS time to be a useful surrogate endpoint for OS time in this indication (33).

In addition, especially in China, OS time data may be confounded by a cross-over and/or secondand third-line treatments, while the treatment effect on PFS time is not confounded by these factors. The PFS as primary endpoint has been well recognized and accepted as a surrogate endpoint by the Chinese Health Authority. Therefore, PFS is considered as an acceptable primary endpoint for this trial.

The endpoint of PFS time will be assessed by an IRC to mitigate any Investigator bias in determining PFS time in this open-label trial. Progression-free survival, as assessed by the Investigator, will be one of the secondary endpoints.

5.3 Selection of Trial Population

Subjects who have recurrent and/or metastatic SCCHN excluding nasopharyngeal carcinoma and who have not received chemotherapy for recurrent and/or metastatic SCCHN.

Only persons meeting all inclusion criteria and no exclusion criteria may be enrolled into the trial as subjects. Before performing any trial assessments not part of the subject's routine medical care, the Investigator will ensure that the subject or the subject's legal representative has provided written informed consent following the procedure described in Section 9.2.

5.3.1 Inclusion Criteria

For inclusion in the trial, subjects should fulfill all of the following inclusion criteria:

- 1. \geq 18 years of age.
- 2. Histologically and/or cytologically confirmed diagnosis of SCCHN.
- 3. Recurrent and/or metastatic SCCHN, not suitable for local-regional treatment. Subjects with recurrent disease only (no metastases) must have received prior radiotherapy (as adjuvant treatment after surgery or as treatment for locally advanced SCCHN) as part of "loco-regional treatment", and the radiotherapy and the radiotherapy must have been completed more than 6 months before screening imaging.
- 4. Presence of at least 1 measurable lesion according to RECIST version 1.1.
- 5. Signed written informed consent before any trial-related activities are carried out.
- 6. ECOG performance status of 0 or 1.
- 7. Neutrophils $\ge 1.5 \times 10^9$ /L, platelet count $\ge 100 \times 10^9$ /L, and hemoglobin ≥ 90 g/L.
- 8. Total bilirubin $\le 2 \times$ upper limit of normality (ULN); aspartate aminotransferase (AST) and alanine aminotransferase (ALT) $\le 3 \times$ ULN (if liver metastasis exists, ALT and AST $\le 5 \times$ ULN).
- 9. Serum corrected calcium, potassium and magnesium corrected within normal range (electrolyte correction is permitted during screening).
- 10. Creatinine clearance ≥60 mL/minute (24 hours creatinine clearance might be requested by the Investigator for confirmation, if calculated creatinine clearance is <60 mL/min).

11. Effective contraception if procreative potential exists (applicable for both male and female subjects) until at least 3 months after the last dose of trial treatment.

5.3.2 Exclusion Criteria

Subjects are not eligible for this trial if they fulfill any of the following criteria:

- 1. Prior systemic chemotherapy, except if given as part of multimodal treatment for locally advanced SCCHN that was completed more than 6 months before randomization.
- 2. Major surgery or irradiation within 4 weeks before randomization.
- 3. Previous treatment with monoclonal antibody or signal transduction inhibitors targeting EGFR.
- 4. Nasopharyngeal carcinoma.
- 5. Known allergic reaction against any of the components of the trial treatment.
- 6. Active infection including active tuberculosis, known and declared human immunodeficiency virus (HIV) infection, or active hepatitis B/C virus (HBV/HCV) infection resulting in an impaired liver function or cirrhosis (see Section 7.2.4).
- 7. History of organ allograft, autologous/allogeneic stem cell transplantation, and renal replacement therapy.
- 8. Asymptomatic severe hypertension or hypertensive crisis defined as systolic blood pressure ≥180 mmHg and/or diastolic blood pressure ≥110 mmHg under resting conditions.
- 9. Impaired cardiac function, evidenced by any of the following conditions:
 - o Left ventricular ejection fraction < 45%
 - Serious arrhythmia
 - Unstable angina pectoris
 - o Congestive heart failure New York Heart Association class III or IV
 - o Myocardial infarction within the 12 months before randomization
 - o Pericardial effusion.
- 10. Known central nervous system metastasis and/or leptomeningeal disease. Subjects with neurological symptoms should undergo a CT/MRI of the brain to exclude brain metastasis.
- 11. Known uncontrolled diabetes mellitus, pulmonary fibrosis, interstitial lung diseases, acute pulmonary diseases, or liver failure.
- 12. Peripheral neuropathy or hearing loss ≥Grade 2.
- 13. Subjects not recovered from any acute effects of prior surgery, chemotherapy, or radiation therapy, that is, to \leq Grade 1 (CTCAE, version 4.03). Chronic late toxicities resulting from

prior radiation and/or surgery (pharyngeal/laryngeal toxicity, i.e., xerostomia, speech, swallowing abnormalities etc.) are permitted if nutritional status is stable.

- 14. Known alcohol and/or drug abuse.
- 15. Medical or psychological condition that would not permit the subject to complete the trial or sign informed consent.
- 16. Past or current history of neoplasm other than SCCHN, except for curatively treated nonmelanoma skin cancer, in situ carcinoma of the cervix, or other cancer curatively treated and with no evidence of disease for at least 5 years.
- 17. Any investigational medication within 30 days before randomization.
- 18. Female subjects who are pregnant (absence to be confirmed by serum β-human chorionic gonadotropin [HCG] test) or breast feeding, or males and females of reproductive potential not willing or not able to employ a highly effective method of birth control/contraception to prevent pregnancy from 2 weeks before receiving trial treatment until 3 months after receiving the last dose of trial treatment. A highly effective method of contraception is defined as having a low failure rate (< 1% per year) when used consistently and correctly.
- 19. Concurrent treatment with a prohibited medication (see Section 6.5.2).
- 20. Subjects with any concurrent medical condition or disease that will potentially compromise the conduct of the trial at the discretion of the Investigator.
- 21. Legal incapacity or limited legal capacity.

Subjects must fulfill all eligibility criteria to be enrolled in this trial. No exemption from any inclusion and exclusion criteria will be allowed. If any deviation from eligibility is retrospectively detected for an already enrolled subject, the Investigator and Sponsor must decide immediately whether it is safe to treat this subject further within the trial (see Section 5.4.2).

5.4 Criteria for Subject Withdrawal

5.4.1 Withdrawal from Trial Therapy

A subject must be withdrawn from all trial treatment (cetuximab and chemotherapy) in the event of any of the following but should stay in the trial:

- Occurrence of an exclusion criterion that is clinically relevant and affects the subject's safety and discontinuation is considered necessary by the Investigator and/or Sponsor.
- Occurrence of AEs and discontinuation of trial treatment is desired or considered necessary by the Investigator and/or the subject.
- Occurrence of pregnancy during trial treatment.
- Occurrence of PD according to RECIST version 1.1.

Document No. CCI	
Object No.	

- Intake of prohibited medications, as defined in Section 6.5.2, if deemed necessary by the Investigator and/or Sponsor.
- Non-compliance.

In case of premature withdrawal from the trial treatment for reasons other than PD, the subjects will be asked to attend scheduled visits until an assessment of PD as planned.

5.4.2 Withdrawal from the Trial

Upon death or loss of follow-up, subjects may be considered as having completed the trial. Subjects may withdraw from the trial at any time without giving a reason. Withdrawal of consent will be considered withdrawal from the trial.

A subject must be withdrawn if any of the following occur during the trial:

- Withdrawal of consent.
- Participation in another clinical trial (In this case, collection of survival data should continue).

If a subject has failed to attend scheduled trial assessments, the Investigator must determine the reasons and the circumstances as completely and accurately as possible, and record the reasons in appropriate sections of the electronic case report form (eCRF).

5.5 Premature Termination of the Trial

The whole trial may be discontinued prematurely in the event of any of the following:

- New information leading to unfavorable risk-benefit judgment of the IMP, such as:
 - o Evidence of inefficacy of the IMP,
 - Occurrence of significant previously unknown adverse reactions or unexpectedly high intensity or incidence of known adverse reactions, or
 - o Other unfavorable safety findings.
- Sponsor's decision that continuation of the trial is unjustifiable for medical or ethical reasons.
- Poor enrollment of subjects making completion of the trial within an acceptable time frame unlikely.
- Discontinuation of development of the Sponsor's IMP.
- Withdrawal of IMP from the market for safety.

Health Authorities and Independent Ethics Committees (IECs)/Institutional Review Boards (IRBs) will be informed about the discontinuation of the trial in accordance with applicable regulations.

The clinical trial may also be terminated or suspended upon request of Health Authorities.

5.6 Definition of End of Trial

The trial will be terminated when the last subject has discontinued the trial treatment or OS cut-off, whichever is later.

The OS cut-off will occur when the following conditions are met:

- Follow-up after the randomization of the last subject is at least 12 months, OR
- At least 180 deaths have been reported in this trial.

Investigational Medicinal Product and Other Drugs Used in the Trial

In this trial, trial treatment consists of cetuximab and cisplatin plus 5-FU. Cetuximab is considered as the IMP and cisplatin plus 5-FU as the background first-line standard chemotherapy for recurrent and/or metastatic SCCHN. If cisplatin results in a nonhematologic toxicity (see Section 6.4.1.2.2), cisplatin may be replaced by carboplatin in subsequent cycles.

Cisplatin, carboplatin, and 5-FU are commercially available cytotoxic agents for the treatment of various cancers, including SCCHN. The chemotherapeutic drugs for this trial will be supplied by the local pharmacy/the third party vendor at each trial center. The Sponsor will provide financial compensation for the cost of chemotherapeutic drugs depending on the procedures of each participating center.

6.1 Description of Investigational Medicinal Product

Cetuximab will be made available in ready-to-use 20 mL vials containing 5 mg/mL solution.

Cetuximab (Erbitux®) 5 mg/mL is manufactured by the Sponsor, packed, labeled and distributed for clinical trial supply by a suitable service provider, and finally released by the Sponsor under GMP conditions

Cetuximab 5 mg/mL gained approval from the European Medicines Agency in March 2007 and a licence for first-line SCCHN in the European Union in November 2008. This formulation of cetuximab does not require filtration before administration. Cetuximab is formulated as 5 mg protein/mL in glycine/sodium chloride/tween/citrate buffer solution at pH 5.5 ± 0.2 , and is aseptically filled in sterile glass vials.

Batch numbers will be provided in the certificates of release. From the documentation of cetuximab, it will be possible to retrace the composition and pharmaceutical quality according to current GMP guidelines. The Sponsor will provide cetuximab free of charge for all eligible subjects.

Dosage and Administration

6.2.1 Selection and Timing of Cetuximab

Subjects in Arm A only, will receive cetuximab in combination with cisplatin or carboplatin plus 5-FU chemotherapy. Cetuximab will be given every 7 days as outlined in Table 6.1.

Table 6.1 Dose and Administration Procedure for Cetuximab

	Dosage	Infusion rate	Flush of line with saline solution (0.9%) at the end of infusion	Prophylactic pretreatment with an appropriate antihistamine and corticosteroid
First infusion	400 mg/m ²	maximum 5 mg/minute	Yes	Mandatory
Subsequent infusions	250 mg/m ²	maximum 10 mg/minute	Yes	Recommend

The cetuximab dose will be based on the subject's BSA and has to be recalculated and the dose adjusted accordingly before each cetuximab infusion. The BSA should be calculated according to the Mosteller formula: BSA (m^2) = sqrt ([height (cm) × weight (kg)] / 3600). The calculation will be based on the weight measured at each relevant visit and the height as measured and recorded at the screening visit.

The maximum infusion rate must NOT exceed 5 mg/minute for first infusion and must NOT exceed 10 mg/minute at subsequent infusions.

Cetuximab will always be administered before cisplatin or carboplatin on Day 1 of a cycle. Cetuximab infusions should be performed, if possible, on the same day of each week with no more than 3 days deviation.

Pretreatment with an appropriate antihistamine and a corticosteroid are mandatory at least 1 hour before the first cetuximab administration and these premedications are recommended before all subsequent infusions of cetuximab (see Section 6.4.2).

Before, during, and up to 1 hour after each cetuximab infusion, subjects must have their vital signs continuously monitored to detect any AEs (specifically, allergic/hypersensitivity reactions). A physician should be available during each cetuximab administration, i.e., until the complete infusion has been given and for 1 hour after the end of the infusion. Exact documentation of actual dose, date, start time, and end time of each cetuximab infusion is mandatory.

Cetuximab must not be mixed with any other substance and therefore requires a separate infusion line. If another intravenous infusion is required at the same time as the cetuximab infusion (e.g., for hydration), a second line must be used.

All subjects randomized to Arm A will receive cetuximab until radiographically documented PD, as assessed by the Investigator, or unacceptable toxicity occurs, or consent is withdrawn. If chemotherapy is delayed, administration of cetuximab every 7 days is continued. If chemotherapy is discontinued for any reason, treatment with cetuximab monotherapy every 7 days is continued.

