Subjects in both arms will receive a maximum of 6 cycles of chemotherapy of 75 mg/m^2 cisplatin as intravenous infusion (refer to China package insert) on Day 1 of each 21-day treatment cycle, and then 750 mg/m^2 /day of 5-FU as a continuous intravenous infusion over 24 hours \pm 6 hours a day from Day 1 to Day 5 of each 21-day treatment cycle.

In the case of cisplatin-related nonhematologic toxicity, cisplatin may be replaced by carboplatin at a dose of target area under the serum concentration time curve of 5 in subsequent cycles. The decision needs to be made in discussion with the Medical Monitor on a case-by-case basis. Carboplatin will be administered using an intravenous infusion of 15 minutes or longer, and in accordance with the China package insert on Day 1 of each 21-day treatment cycle.

Planned treatment duration per subject:

The treatment duration per subject may vary. Subjects will be treated with a maximum of 6 cycles of chemotherapy and/or cetuximab weekly in the absence of PD, as assessed by the Investigator, and unacceptable toxicity. Subjects (in Arm A) who demonstrate at least a tumor response of stable disease (RECIST version 1.1) after 6 cycles of trial treatment will continue monotherapy with cetuximab until either PD or occurrence of unacceptable toxicity. Subjects who stop treatment before reaching PD will continue to have tumor assessments (CT or MRI) every 6 weeks until either PD, the start of a new antitumor treatment, death, or termination of the trial, or loss of follow up, whichever comes first. Upon occurrence of PD, all trial treatments should be discontinued.

Sample Size Calculation: CCI

Randomization: Randomization will be performed centrally using an interactive web response system (IWRS). A central stratified permuted block randomization procedure will be used to balance between treatment arms. The stratification factors are ECOG performance status (0 versus 1) and the primary tumor site (oral cavity versus hypopharynx versus others).

Statistical Analyses:

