5.1 Overall Trial Design and Plan

This multicenter, open-label, randomized, parallel-group, phase III trial will randomize approximately 240 subjects with recurrent and/or metastatic SCCHN and involve approximately 30 trial centers in China. The overall trial design is illustrated in Figure 5.1.

Figure 5.1 **Schematic of the Trial Design** Screening **Treatment Period*** Safety Follow-up Period Survival Follow-Period up Cisplatin/Carboplatin+5-Cetuximab Safety assessment will be FU every 21 days / Max monotherapy performed 30 days (± 3 of 6 cycles Within 28 2 days) after the last dose of + Cetuximab weekly Survival status and days before trial treatment or subsequent trial immediately before starting anticancer therapy Cisplatin/Carboplatin+5treatment any new antitumor treatment FU every 21 days / Max starts of 6 cycles Safety Follow-up Eligibility Efficacy assessments End of efficacy visit every 6 weeks until PD confirmation assessment * *: This can be done after safety follow-up

5-FU: 5-fluorouracil, PD: progressive disease.

All eligible subjects will be randomized to 1 of 2 treatment arms in a 2:1 ratio:

- Arm A (cetuximab plus chemotherapy): Combination of cetuximab and cisplatin plus 5-FU. Subjects who are without progressive disease (PD) after 6 cycles of treatment will continue monotherapy with cetuximab until occurrence of PD or unacceptable toxicity.
- Arm B (chemotherapy alone): Cisplatin plus 5-FU only.

Randomization will be performed centrally using an interactive web response system (IWRS). Randomization will be stratified according to ECOG performance status (0 versus 1) and the primary tumor site (oral cavity versus hypopharynx versus others) (see Section 6.3).

Definition of treatment cycle: The ideal cycle in each arm is 21 days long and is determined by the chemotherapy as follows:

- Arm A: 1 treatment cycle consists of dosing with chemotherapy plus cetuximab on Day 1, and doses of cetuximab on Days 8 and 15, with follow-up through to Day 21 of the cycle.
- Arm B: 1 treatment cycle consists of dosing with chemotherapy staring from Day 1 of each cycle.

The regimen of cetuximab for subjects in Arm A is shown in Table 6.1. Subjects in Arm A and B will receive the same chemotherapy regimen **every 21 days**, which is based on cisplatin plus 5-FU and is shown in Table 6.4.

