Duration of treatment for subjects in Arm A: Subjects with absence of PD, as assessed by the Investigator, and unacceptable toxicity will receive a maximum of 6 cycles of chemotherapy (cisplatin plus 5-FU) and cetuximab weekly. Subjects who have not experienced PD after end of chemotherapy will continue treatment with cetuximab until either PD, as assessed by the

Investigator, or occurrence of an unacceptable toxicity. Subjects with an unacceptable toxicity due to one of the trial drugs will receive other trial drug(s) without unacceptable toxicity until either PD or completion of 6 cycles of chemotherapy. If treatment with cetuximab is delayed because of a related toxicity, the 21-day rhythm of chemotherapy is retained. A maximum of 2 consecutive cetuximab infusions can be withheld (no more than 21+3 days without cetuximab infusions) due to unacceptable toxicity, otherwise the subject must stop cetuximab. If treatment is delayed because of toxic effects of the chemotherapy, the 7-day rhythm of cetuximab infusions is retained. Chemotherapy can be delayed for a maximum of 21+3 days; after this, the subject must stop the chemotherapy treatment. The subject may continue on cetuximab monotherapy (if still benefiting).

Duration of treatment for subjects in Arm B: Subjects with absence of PD, as assessed by the Investigator, and unacceptable toxicity will receive a maximum of 6 cycles of chemotherapy. Subjects with an unacceptable toxicity due to one of the trial drugs will receive other trial drug(s) without unacceptable toxicity until either PD, as assessed by the Investigator, or completion of 6 cycles of chemotherapy. Chemotherapy can be delayed for a maximum of 21+3 days; after this, the subject must stop the chemotherapy treatment.

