6.4.1.1.4 Criteria for Starting the Next Cycle of Chemotherapy

Before starting the next cycle of chemotherapy, the following criteria must be fulfilled:

- Absolute neutrophil count (ANC) is $\ge 1.5 \times 10^9 / L$.
- Platelet count is $\geq 100 \times 10^9 / L$.
- Nonhematologic chemotherapy-related toxicities have resolved to ≤ Grade 1 or baseline (excluding weight loss, skin reactions, paronychia, fatigue, ototoxicity or neurotoxicity which must have resolved to ≤ Grade 2).

If these criteria are not met, the start of the next cycle must be delayed to allow for recovery. If a delay of more than 21 days is necessary as a result of an unresolved toxicity, one or both of the chemotherapeutic drugs should be discontinued.

If the start of the next cycle must be delayed due to either a cisplatin/carboplatin-, or 5-FU-related toxicity, the start of the other compound should also be postponed. However, if either cisplatin/carboplatin or 5-FU dosing must be permanently discontinued, dosing should be continued with the remaining compound according to the schedule.

The BSA must be recalculated and the cisplatin and 5-FU doses adapted accordingly before each subsequent cycle (for formula see Section 6.4.1.1.1). A delay in the next cycle of up to 3 calendar days from the calculated Day 1 of that cycle for administrative reasons such as a weekend is at the discretion of the treating Investigator.

For those in Arm A, in case of cetuximab-related toxicity, chemotherapy will not be delayed and the planned schedule for administration should be maintained. If cetuximab treatment is terminated for a cetuximab-related toxicity, chemotherapy will be continued. If chemotherapy is completely terminated for a related toxicity, cetuximab may be continued as monotherapy until either PD, as assessed by the Investigator, an unacceptable toxicity or withdrawal of consent.

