6.4.1.2 Dose Reductions of Chemotherapy

Every effort will be made to administer the full doses of cisplatin/carboplatin and 5-FU.

Dose reductions are always based on the dose of the previous cycle. Only 2 dose reductions for cisplatin and 5-FU and 1 dose reduction for carboplatin are permitted. If further toxicity occurs or the criteria for resuming treatment are not met, the subject must be withdrawn from chemotherapy (see Table 6.5).

Table 6.5 Dose Reductions for Chemotherapy

	Dose reduction levels	Dosage ¹
Cisplatin	0	75mg/m ²
	-1 (decreased by 20%)	60mg/m ²
	-2 (decreased by 20% from -1 level)	48mg/m ²
Carboplatin ² -	0	AUC 5
	-1 (decreased by 20%)	AUC 4
5-Fluorouracil	0	750mg/m ²
	-1 (decreased by 20%)	600mg/m ²
	-2 (decreased by 20% from -1 level)	480mg/m ²

Abbreviation: AUC, area under serum concentration time curve.

- 1 The doses which have been reduced for toxicity must not be re-escalated.
- 2 Carboplatin can be considered, if the subject experiences a nonhematologic toxicity. The starting dose of carboplatin would be the first dose level of AUC 5 at the Investigator's discretion.

Dose adjustments are to be made according to the body system showing the greatest degree of toxicity experienced during the previous cycle. Toxicities will be graded using the CTCAE version 4.03.

All implemented dose reductions are permanent. The doses must be modified according to the lowest hematology values and the highest degree of nonhematologic toxicities observed at the scheduled date of chemotherapy. If a subject develops several different toxic effects and there are conflicting recommendations, the dose modification will be based on the AE on the scheduled day of treatment.

Dose reduction and delays and related management will be documented in the subject's medical record and in the related section in the eCRF.

If a subject has a Grade 3 or 4 toxicity after 2 dose reductions, or if a treatment delay is longer than 3 consecutive weeks, then the discontinuation of chemotherapy treatment has to be considered.

For those in Arm A, chemotherapy will not be delayed for cetuximab-related toxicities.

Major toxicities observed with cisplatin: nephrotoxicity; ototoxicity; myelodepression with leukopenia, thrombocytopenia and anemia; infectious complications; nausea and vomiting; and peripheral neuropathies.

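### The protocol gives conflicting instructions for when chemotherapy is stopped for toxicity without progression, including whether cetuximab in Arm A must or may go on

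*Protocol*

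**What the plan says.** **Cetuximab after chemotherapy stops (Arm A).** Protocol 6.2.1 states: "If chemotherapy is discontinued for any reason, treatment with cetuximab monotherapy every 7 days is continued". The same paragraph sets the general duration: "All subjects randomized to Arm A will receive cetuximab until radiographically documented PD", with unacceptable toxicity or withdrawal of consent as the only other end points. Section 6.4.1.1.4 uses optional wording: "If chemotherapy is completely terminated for a related toxicity, cetuximab may be continued as monotherapy until either PD". Section 6.2.2.3 is also optional. Section 5.1 permits monotherapy after chemotherapy has been stopped for an over-long delay, on condition that the subject is still benefiting. The same 5.1 paragraph says that a subject with unacceptable toxicity from one trial drug "will receive other trial drug(s) without unacceptable toxicity until either PD or completion of 6 cycles of chemotherapy".

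**Cytotoxic drugs (both arms).** After setting the number of permitted reductions, 6.4.1.2 says: "If further toxicity occurs or the criteria for resuming treatment are not met, the subject must be withdrawn from chemotherapy". Later in 6.4.1.2, and again in 6.4.1.2.2, Grade 3 or 4 toxicity after two reductions, or a delay of more than three weeks, means only that stopping has to be considered. Section 6.4.1.1.4 treats the drugs separately: if either platinum or 5-FU "dosing must be permanently discontinued, dosing should be continued with the remaining compound according to the schedule".

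**Length of delay.** Section 5.1 allows 21+3 days, after which chemotherapy must stop. Section 6.4.1.1.4 acts after more than 21 days and stops one or both drugs. SAP Appendix 1 lists continuing chemotherapy after a toxicity delay of more than 21 days as an important deviation.

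**Entry to maintenance.** The synopsis refers to Arm A subjects "who demonstrate at least a tumor response of stable disease (RECIST version 1.1) after 6 cycles of trial treatment will continue" on cetuximab alone. Section 5.1 says: "Subjects who are without progressive disease (PD) after 6 cycles of treatment will continue monotherapy with cetuximab".

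**The concern.** Cetuximab continued beyond chemotherapy is part of the experimental strategy, and the effect of that strategy on IRC-assessed PFS is the primary endpoint. The trial is read as positive on a point estimate alone: a stratified hazard ratio of 0.77 or less, with no hypothesis test. If one section requires continuation and others leave it to choice, two sites can treat the same Arm A subject differently and each cite the protocol. The trial is open-label, so that choice is made knowing how the subject is doing.

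The cytotoxic rules raise a second problem. A site can follow one section and be in breach of another, so the deviation listing may record departures that the protocol itself permits.

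**Working it through.** There is no figure in the plan to reproduce. The check sets the instructions side by side for a subject without PD.

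| Situation | Section | Instruction |
|---|---|---|
| Arm A, all chemotherapy stopped for toxicity, cetuximab tolerated | 6.2.1 | cetuximab continues, whatever the reason |
| | 6.2.2.3, 6.4.1.1.4 | cetuximab may continue |
| | 5.1 (after over-long delay) | may continue if still benefiting |
| Permitted reductions used up, Grade 3 or 4 toxicity recurs | 6.4.1.2, first statement | must leave chemotherapy |
| | 6.4.1.2, later statement; 6.4.1.2.2 | stopping has to be considered |
| | 6.4.1.1.4, if one drug is permanently stopped | the other drug continues |
| Toxicity delay of 22 to 24 days | 5.1 | within the limit |
| | 6.4.1.1.4 | one or both drugs should stop |
| | 6.4.1.2, 6.4.1.2.2 | stopping has to be considered |
| | SAP Appendix 1 | continuing is an important deviation |

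**First situation.** A site that continues cetuximab satisfies every section. A site that stops it, with no PD, no unacceptable toxicity and no withdrawal of consent, satisfies 6.2.2.3 and 6.4.1.1.4 but contradicts 6.2.1. The conflict therefore matters where a site chooses to stop.

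**Second situation.** The two statements in 6.4.1.2 overlap for Grade 3 or 4 toxicity after two reductions and give different duties. The first speaks of chemotherapy as a whole, whereas 6.4.1.1.4 and the dose-reduction lines in SAP Appendix 1 work drug by drug.

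**Third situation.** 21 + 3 = 24 days against 21 days, so the disputed window is days 22 to 24.

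**Maintenance entry.** Measurable disease is required (inclusion criterion 4), so at least stable disease and absence of PD separate only when the scan at that visit is not evaluable. This is minor.

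**Illustration for one Arm A subject.** Assume chemotherapy stops for toxicity after cycle 3 (3 × 3 = week 9), cetuximab is tolerated, and PD occurs at 5.6 months, the combination-arm median that the protocol quotes from the EXTREME trial.
- Time to PD: 5.6 × 30.4375 / 7 = 24.35 weeks.
- Further weekly infusions if cetuximab continues to PD: 24.35 − 9 = 15.35, about 15.
- Further infusions if the optional wording is used to stop: 0.

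The stop time is an assumption, and the result shifts one for one with it.

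**Would the planned analyses isolate this?** Every treatment-continuation line in SAP Appendix 1 is marked as not clinically important, and none is directed at stopping cetuximab because chemotherapy ended. The nearest, more than 24 days off cetuximab, is also not clinically important. The per-protocol set would not remove such subjects on this ground.

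**The case against.** Some discretion after toxicity is ordinary in oncology, and a strategy that includes it can still be estimated. The primary analysis is ITT as randomized. Imaging continues after treatment stops for reasons other than PD, until PD, new antitumor treatment, death, loss to follow-up or the end of the trial. SAP 12.1 reports discontinuation and its reason by drug, and SAP 15.1 reports cetuximab duration, cumulative dose and dose intensity, so variation would be visible in aggregate. All of this stands. It limits the consequence but does not make the instructions agree.

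A reader might infer from 5.1 that cetuximab is capped at six cycles (6 × 21 = 126 days, or 18 weeks) once chemotherapy is stopped for toxicity. The documents do not support that securely. The same paragraph continues cetuximab after the end of chemotherapy until PD or unacceptable toxicity, and allows monotherapy after an over-long delay. The clause recurs almost unchanged for Arm B, where only cytotoxics are given. A subject who has stopped all chemotherapy also never completes six cycles of it. The wording does not exclude cetuximab from the other trial drugs, so it needs clarifying, but no infusion count should be built on it.

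A reader might also infer that the cytotoxic conflicts change cetuximab exposure. They apply to both arms and do not in themselves alter how long cetuximab is given.

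**Conclusion.** The contradictions are real and in current protocol text. The clearest is whether cetuximab must or may continue in Arm A after chemotherapy stops for toxicity. Next are the duty to stop or only consider stopping chemotherapy, the fate of the remaining cytotoxic, and the 21- versus 24-day limit. The maintenance-entry wording is a small addition.

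The size cannot be stated for the trial. The documents do not give the number of Arm A subjects who stop all chemotherapy for toxicity without PD. A reader might take an assumed rate of early chemotherapy stopping as the number affected, but that rate would include subjects stopping for PD, in whom all trial treatment ends and no conflict arises. The 0-versus-15 contrast is one subject under stated assumptions.

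Nor do the documents show any shift in the hazard ratio or in the chance of meeting 0.77. The ITT comparison remains valid. What is lost is a single, clearly described experimental strategy and consistent deviation coding. It should be corrected.

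**What to change.** Reconcile the synopsis and Protocol 5.1, 6.2.1, 6.2.2.3, 6.4.1.1.4, 6.4.1.2 and 6.4.1.2.2 so that each of these has one instruction, worded identically wherever it appears:
- cetuximab after chemotherapy is stopped for toxicity;
- further toxicity after the permitted reductions, and whether the remaining cytotoxic continues;
- the maximum chemotherapy delay and its consequence;
- entry to cetuximab maintenance, including a not-evaluable scan.

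State whether the completion-of-six-cycles clause in 5.1 applies to cetuximab. Then align the continuation and delay lines in SAP Appendix 1 with the result. Which rule applies in each case is for the sponsor's clinicians.

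The drafting cost is small and no analysis changes. Rules on continuing treatment may count as a substantive amendment under Protocol 10.5 and need submission. Recruitment was planned to end in the fourth quarter of 2017 and the SAP rests on a protocol version dated 26 February 2018, so new wording would mainly help subjects still on treatment and settle deviation coding before database lock.
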